Version #1, 12/14/15

Page 8 of 17

Management begins with adjustment of the time of administration of study and concomitant medication (e.g. changing valproic acid from 750 mg BID to 500 qAM and 1000 mg qHS) and sleep hygiene instructions (Appendix A). This approach is common clinical practice in patients with bipolar disorder. If this does not improve sleep, then melatonin is added. If this approach is not successful, then trazodone is added. Although trazodone is an antidepressant in high doses, a review of the literature does not reveal evidence of either improvement in depressive symptoms or induction of manic symptoms at modest nighttime doses. The next step is the use of ramelteon (a prescription melatonin receptor agonist). If these approaches fail to control the insomnia, then the combination of ramelteon and trazodone will be allowed. It is also important to note that insomnia is frequently a transient side effect with aripiprazole. Data from large aripiprazole trials suggest that the incidence of insomnia decreased from approximately 12% at week 1 to 5% at week 3 in patients who continued in the trials.⁵⁷ Thus, it may resolve in many cases without the use of concomitant medications.

Insomnia Management Algorithm

- 1) Adjustment of timing of administration of study drug and concomitant medications, current medications AND sleep hygiene instructions.
- 2) Melatonin
 - a. Begin melatonin at 3mg po qHS—to be taken one to two hours prior to bedtime.
 - b. If no significant improvement in insomnia, increase melatonin to 6mg po qHS—to be taken one to two hours prior to bedtime.
 - c. If no significant improvement, discontinue melatonin and proceed to step #3.
- 3) Trazodone
 - a. Begin trazodone at 25mg po qHS—to be taken 30-60 minutes prior to bedtime.
 - b. If no significant improvement in insomnia, increase trazodone as tolerated to 50mg po qHS.
 - c. If no significant improvement in insomnia, increase trazodone as tolerated to 100mg po qHS.
 - d. If no significant improvement in insomnia, discontinue trazodone and proceed to step #4.
- 4) Ramelteon
 - a. Begin ramelteon at 8mg po qHS—to be taken 30-60 minutes prior to bedtime.
 - b. If no significant improvement, proceed to step 5.
- 5) Combination therapy using ramelteon and trazodone.

Fatigue and disturbance in attention may both be related to the sedating properties of aripiprazole. It appears to be a medication that can cause restlessness and insomnia, as well as fatigue, sedation and somnolence. These daytime side effects of aripiprazole will be managed as described above with 1) timing of study drug dosing (qHS rather than morning), and 2) adjustments in timing of concomitant medications (e.g. greater proportion of total dose in early evening than in the morning).

Finally, although not as common as the above side effects, nausea and vomiting are sometimes reported with aripiprazole. Nausea was uncommon in our pilot study (section 3.3.a) and in the aripiprazole study in alcohol dependence²⁵ but, perhaps due to the higher starting dose, was observed with greater frequency than placebo in the bipolar depression trial.⁴² We will minimize this side effect with a low-starting dose and the use of a slower dose titration when needed. If nausea is reported, the participants will be instructed to take the study drug with a meal (per package insert aripiprazole can be taken with or without food).

Please note that all side effect management will be conducted in a double-blind fashion. In all of the aripiprazole trials noted above, side effects were also reported in the placebo group. Thus, the development of side effects does not necessarily suggest that the participant is taking aripiprazole.

In order to minimize the risks related to the use of placebo, we will schedule frequent appointments with a psychiatrist investigator and research coordinator. If participants have a worsening of symptoms, such as active suicidal ideation, study participation will be discontinued, and we will provide them with referrals for appropriate care.

All investigators and research staff will be available 24 hours a day. The consent form will have both daytime and nighttime numbers for reaching study personnel. Business cards for the research coordinator and psychiatrists will also be provided. In the event an investigator or research coordinator is on vacation or out-of-town, coverage will be provided, and both the research coordinator and UT Southwestern answering service are informed of the name and pager number of the physician-on-call. In the event of a medical or psychiatric emergency, appropriate medical advice will be provided including recommendations for emergency room evaluation if necessary. The PI and other physicians involved with the study have staff privileges at the Parkland and William P. Clements University Hospital Emergency Rooms, which are likely to be the most

commonly used hospitals by the participants. The physicians and other staff have extensive experience working with patients with bipolar disorder and substance use disorders.

All women of childbearing potential (premenopausal and without a clearly documented hysterectomy, ovariectomy or bilateral tubal ligation) must have a urine pregnancy test with negative results prior to receiving study medication. These participants will also be asked to use effective forms of contraception during the study. Pregnancy or failure to use contraceptives will result in discontinuation from the study.

Potential safety concerns will result in discontinuation from the study protocol. However, standard care will be provided until referral to another physician for further care can be arranged. The following conditions would require consideration of discontinuation from the study:

- Change in diagnosis to other than bipolar I, II, or NOS disorder and AUD.
- Development of active suicidal or homicidal ideation with plan and intent.
- Worsening in mood symptoms, that in the opinion of the investigators requires discontinuation.
- Pregnancy.
- Development of severe or life-threatening medical condition.
- Involuntary psychiatric hospitalization or incarceration.
- Significant alcohol withdrawal (e.g. delirium tremens) based on clinical judgment. Increases in CIWA-Ar scores will initiate a careful clinical assessment of possible worsening of withdrawal symptoms.

These are general guidelines. In all cases, physician judgment will be used to determine whether or not a participant can safely remain in the study. Some level of suicidal ideation is common in the participants we research. However, we want to take steps to prevent risk of suicidal acts. Thus, the emergence of intense suicidal thoughts with a clear plan (e.g. overdose) and the intent to act on the plan would require discontinuation from the study. However, recurrent suicidal thoughts accompanied by a clear understanding that the participant does not plan to act on these thoughts would not require discontinuation.

A breathalyzer will be used to assess whether or not the participant is currently intoxicated (defined in Texas as a blood alcohol level $\geq 0.08\%$). On rare occasions, patients in our alcohol treatment studies have arrived at our clinic intoxicated. We handle this on a case-by-case basis by asking them to remain at our clinic for several hours until their blood alcohol level has decreased and, if necessary, later calling a friend to take them home. We do not allow participants to leave our clinic while intoxicated. If a patient insisted upon leaving the clinic while intoxicated, we would call campus police.

For participant safety and the internal validity of the study, concomitant medications for bipolar disorder will be managed in order to prevent discontinuation due to symptoms unrelated to the primary outcome of alcohol use, while providing consistency and structure to the medication management.

The proposed study is placebo-controlled and in a group of patients with a major mental illness and substance abuse. Given the potentially vulnerable nature of the participants, in addition to the monitoring and review by the UT Southwestern IRB, we have implemented an additional data and safety monitoring plan that includes the formation of a Data and Safety Monitoring Board (DSMB).

Adverse Events

- 1) Exclusion criteria include active suicidal ideation, pregnant or nursing women, or prisoners to minimize risk to vulnerable populations or adverse events.
- 2) All adverse events will be discussed with and evaluated by a physician investigator as soon as reported by the subject.
- 3) Adverse events will be appropriately reported to the IRB and DSMB. The UT Southwestern IRB Policy it to only accept Adverse Events that are “Unexpected (in terms of nature, severity, or frequency) and Definitely or Probably related *and* Serious or otherwise suggests that the research places subjects or others at a greater risk of harm (including physical, psychological, economic, or social harm) than was previously known or recognized. Serious adverse events meeting these criteria are to be individually reported within two business days to the IRB. We will report serious adverse events to the NIAAA within 24 hours and can also report these adverse events to the IRB within 48 hours rather than two business days. We will report the adverse events that the IRB does not review to the DSMB for the study. Unexpected, but not serious, adverse events will be reported within 5 working days of our being informed by the patient of the occurrence of the event. Nonserious, expected adverse events will be reported to the IRB and DSMB in periodic summary reports. As part of this reporting process, the PI evaluates the severity of the adverse event, its relationship to the study, and whether changes in the protocol are warranted. Adverse events will also be reported to NIAAA in annual progress reports.

- 4) We will also report all AEs occurring during the follow-up period to the NIAAA in an annual report and will report reportable AEs to the IRB. AEs will also be reviewed at DSMB meetings
- 5) In addition to the IRB review of adverse events outlined above, the PI will meet weekly with staff and physicians to discuss any problems that arise that could compromise patient safety. When necessary, the IRB will be consulted for further guidance.
- 6) The PI, co-investigators involved with clinical care and the research coordinators will be available 24 hours each day to patients and other investigators should an emergency arise.

Data and Safety Monitoring Board

In addition to the safeguards listed above, we will form a Data and Safety Monitoring Board that will periodically review the project. This board will consist of [name]., Ph.D. (chair), [name]. and [name] [name].

As for the logistics of the proposed board, we propose that the members be unblinded so they can make a meaningful assessment of the data from both placebo and active medication groups. We currently have ongoing DSMBs for other NIH-funded clinical trials and have proposed a similar design for the proposed board. The board will meet immediately prior to the initiation of enrollment in the study, after 25, 50, 75 and 100 participants have been enrolled, and at the end of the study. The study's biostatistician will present safety data to the board for review, including changes in psychiatric symptom severity and alcohol use/craving. The PI ([name]) will attend the meeting at the beginning and end, but will not be present if any unblinded data are reviewed in order to preserve integrity of the blind. In addition, materials provided to the IRB, including serious adverse events (SAEs) leading to death, hospitalization or ER visits will be forwarded to board members. The board will review preliminary data on adverse events and outcomes. If, based on this review, the board feels that protocol modifications are needed, it will have the authority to modify safety procedures and temporarily or permanently discontinue enrollment if needed. At each DSMB meeting a careful consideration of stopping the study will be conducted. If the number of total SAEs in the aripiprazole group is \geq 3 times higher than with placebo study, the data will be flagged for special consideration by the DSMB. The DSMB will carefully review the SAEs. Additional information, such as scores on each organ system assessed by the PRD-III side effects scale may be requested to guide decision making. The board will then provide written documentation and justification of a decision to continue or stop enrollment. This approach is based on the stopping rules suggested by Hedenmalm et al.⁵⁸ Because stopping rules are often reserved for larger, multisite trials, we modified the recommendations for a smaller study. Instead of using a predetermined significance, such as $p < .001$ to prompt consideration of discontinuation we use the value of three times greater than with placebo. We selected this approach because statistical significance might be virtually impossible to achieve with relatively uncommon, dichotomized events from relatively small numbers of participants. Rather than attempting to categorize the SAEs, which would result in very small numbers in each category, we will use total SAEs to prompt review. At this point the DSMB can review specific types of SAEs and look for patterns. We will review the proposed procedures of the DSMB with the NIAAA program official and seek their guidance and approval prior to enrollment.

12. Procedures to Maintain Confidentiality:

Blood specimens will be provided to Quest Diagnostics for analysis, removing identifying information (e.g., name) that could be linked to the patient's identity prior to sending for analysis. The blood provided to Quest will have the participant's date of birth to correctly link the results to the participant. The results of this test will be de-identified and added to the rest of the de-identified data. Once de-identified, only the identified investigators can learn/discover the names of participant.

Data Management Plan

All data related to the participant's participation in this study will be given a study ID which cannot be traced back to the patient except by study staff. All personal information which can identify the patient's identity will be kept separately from study documents and assessments. All clinical assessments will be collected in paper form and scores transferred to a computer database maintained on a password protected computer, on a secure server behind a firewall. The paper forms will be kept in binders marked only with the patient's study ID and will be kept in a locked room for the required time period following the completion of this study.

A Certificate of Confidentiality will be obtained for this study.

13. Potential Benefits:

Bipolar disorder is a severe, persistent, and common psychiatric illness that is associated with a staggering 46% lifetime prevalence of alcohol-related disorders, being associated with numerous adverse consequences including increased hospitalization, poor outcome during hospitalization, violence towards self and others, and treatment nonadherence. The atypical antipsychotic aripiprazole is a particularly promising medication which may lead to the development of effective treatments for patients with bipolar and alcohol use disorder. This rare placebo-controlled trial in patients with bipolar disorder and alcohol use disorder may be an important step forward toward advancing the successful treatment of this patient population. Minimal data are available on the treatment of persons with BPD and substance abuse. However, these illnesses occur together at high rates. Thus, the primary benefit of the study will be for persons with BPD or schizoaffective disorder bipolar type and alcohol use disorder to determine whether aripiprazole therapy will reduce alcohol use and craving. *There may, however, be some benefit to the subjects who participate in the study as they will receive a careful screening for mood symptoms as well as MM.* Approximately half of the subjects will receive an active medication that, in some cases, will likely improve their mood symptoms.

The primary risks of this study are medication side effects and the risk of receiving inactive medication, though aripiprazole appears to be a generally safe and a reasonably well-tolerated medication. We feel it is essential for this study that a placebo group be included as the efficacy of even standard medications in dual-diagnosis patients is not well established. Thus, the benefits of the study are great and will include a better understanding of the treatment of bipolar disorder with comorbid alcohol use disorder. This will be the first controlled study of this medication in patients with bipolar disorder and alcohol use disorder, and will provide valuable data on its efficacy in this population and the relationship between mood symptoms and drug use. Thus, we feel that the risks, though clearly present, are greatly outweighed by the benefits of this study.

14. Biostatistics:

baseline use of psychotropic medications, and change in use of psychotropic medications. Covariates will be included if they significantly improve the fit of the final model. An a priori alpha of 0.05 will be used for all other analyses. The influence of exit aripiprazole blood levels on the primary, secondary and exploratory aims will also be examined.

Secondary Aim: 1) *Determine if aripiprazole as an add-on therapy is associated with a greater reduction in alcohol craving than placebo therapy in outpatients with BPD or Schizoaffective Disorder (bipolar type) and AUD.* PACS scores will be compared between groups with an ITT sample and using a random regression as described above.

Additional Exploratory Analyses:

1) *Determine if aripiprazole as an add-on therapy is associated with a greater reduction in manic and depressive symptoms than placebo therapy in outpatients with BPD or Schizoaffective Disorder (bipolar type) and AUD.* Between-group differences in YMRS, HRSD₁₇ and IDS-SR₃₀ scores will be compared using a random regression as above.

2) *Determine whether changes in alcohol craving and mood occur before or after changes in alcohol use with aripiprazole.* We will explore correlations between baseline to exit changes in mood (e.g. HRSD₁₇) and alcohol use/craving assessments using a Pearson's correlation coefficient in aripiprazole and placebo groups. In addition, a panel model with lagged effects⁵⁹ will be used to analyze 12-week longitudinal data (SAS Proc Panel) in order to explore serial correlations between changes in alcohol use with mood and craving with lagged effect (e.g. one week, two week). Panel model will be constructed for each alcohol use, alcohol craving, depressive and manic symptom, and cognitive outcome, and test if change in alcohol use follows changes in craving, mood or cognition at subsequent visits and vice versa.

3) *Determine if impulsivity decreases with aripiprazole as compared to placebo and examine relationships between change in impulsivity and change in alcohol consumption.* BIS-11 and GNG scores will be compared between groups as with the Primary Aim above. Correlations between BIS-11 scores and GNG scores, and alcohol use measures, as well as lagged effects will be compared as with Exploratory Aim 2 above.

4) *Assess rates of attrition, safety and tolerability of aripiprazole.* Length of time in the study in weeks will be compared between groups using Cox proportional hazards regression. Scores on the PRD-III, AIMS, BAS and SAS will be compared between-groups as with the Primary Aim above.

5) *Examine genotype as a predictor of response to aripiprazole.* The purpose of this analysis is to identify whether genotype (e.g. 1438A polymorphism in the promoter region of the 5-HT2A receptor, LL compared with the LS/SS of the 5-HTLPR promoter region of the 5-HTT) is a moderator of treatment effect. Treatment effect is determined by treatment group, main effect and treatment group by time interaction effect estimated from the random regression model described for the primary aim. The potential moderator of genotype will be included in the random regression model for the primary outcome along with variable by treatment group interaction and variable by treatment group by time interaction. Significance for either interaction term would indicate that the variable is a moderator.

6) *Explore safety, tolerability and efficacy of an increase in aripiprazole from 15 mg to 30 mg at week 16 for those with at least one drinking day at week 12.* All lab values and other safety measures will be compared between treatment groups at week 16 using t-test or chi-square test, as appropriate. Scores on outcomes measures including alcohol use (e.g. heavy drinking days) and side effect scales (e.g. BAS) will be compared between groups at week 16 using analysis of covariance. Week 12 value of the outcome will be the covariate.

7) *Determine if inflammation decreases with aripiprazole as compared to placebo and whether change in an inflammatory biomarker is associated with change in clinical outcomes.* Analysis described for Exploratory Aim 3 (above) will be used with hs-CRP data to test this aim.

Power analysis: One potential guide to calculate effect size comes from a recent study comparing naltrexone alone and with aripiprazole for alcohol dependence.⁶⁰ The results of that study have not been published yet. However, the abstract shows that the sample size was 21 per group, and the p-value was .009 for a between-group comparison of heavy drinking days. If we assume a two-sample t-test, then from the above information we can compute the smallest value of the quantity (placebo mean – aripiprazole mean) / standard deviation that will produce a p-value of .009. This quantity (i.e. the effect size) is 0.841. This effect size would be classified as a large effect size which may not be reproducible in another sample with a different design and patient population. If we assume a medium effect size of 0.5, 80% power, a two-sided t-test, and

alpha=.05 then a total sample size of 128 would be required. All subjects with post-baseline data, not just completers, will be included in the analysis. However, we frequently see some attrition (approximately 3%) between baseline and the first post-baseline assessment, therefore, final sample size will be 132.

References:

3. Morrison JR. Bipolar affective disorder and alcoholism. *The American journal of psychiatry.* 1974;131(10):1130-3. Epub 1974/10/01. PubMed PMID: 4412212.

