To date, few randomized, controlled trials have specifically examined the pharmacotherapy of patients with BPD and AUD. Thus, more research is much needed in this important population. We examined a group of patients with BPD and substance use disorders (n=20) switched from their current atypical antipsychotic (generally quetiapine) to aripiprazole. Mean depression and manic symptom scores significantly improved. In the subset (n=17) with AUD, the switch to aripiprazole was associated with a reduction in both alcohol use and craving. Aripiprazole was well tolerated. Scores on scales for antipsychotic side effects (akathisia, extrapyramidal symptoms, abnormal movements) did not change significantly. The findings, while preliminary in nature, suggest that aripiprazole may be more effective in reducing alcohol use in patients with BPD and AUD than other atypical antipsychotics. Aripiprazole appears to be a promising potential treatment for AUD. However, its utility may be limited by poor tolerability that may be due to improper dosing, as well as the outcomes and population chosen. To address these problems we propose to 1) use a dual-diagnosis population because aripiprazole is well tolerated and useful for mood symptoms in patients with BPD 2) use a dose of only 15 mg/day except in an exploratory phase, unless the patient qualifies for the exploratory phase or the patient is on strong CYP3A4 inducers which increase aripiprazole clearance and lower blood levels of aripiprazole 3) use participants with high impulsiveness since this may predict a favorable aripiprazole response, and 4) use a primary outcome measure that is sensitive to aripiprazole effects.

3. Concise Summary of Project:

We will conduct a 12-week, randomized, double-blind, parallel-group, placebo-controlled study of aripiprazole in 132 persons with AUD and bipolar I, II, or NOS disorder. Primary Aim will be to assess change in alcohol use by the Timeline Followback (TLFB) method.^{29, 30} Secondary Aim will include change in alcohol craving using the Penn Alcohol Craving Scale (PACS).³¹ Changes in psychiatric symptoms (mania/hypomania and depression) and predictors of response will be assessed. Participants with ≥ 1 drinking day at week 12 will be enrolled in a 4-week extension phase with an upward titration to 30 mg/day for those in the active treatment group. The placebo group will remain on placebo.

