Strong CYP3A4 inducers are the following: Nevirapine, Rifabutin, Rifampicin, Carbamazepine, Fosphenytoin, Pentobarbital, Phenobarbital, Phenytoin, Primidone, Rifapentine, Enzalutamide, Lumacaftor, St. John's Wort, Mitotane, Apalutamide, and Quinine.

Week 1, 2, 3, 5, 7, 9, 10, 11 (~2 hours each): Subjects will complete the YMRS, HRSD₁₇, CIWA-Ar, TLFB, IDS-SR₃₀, PACS, PRD-III, AIMS, BAS, SAS, and a urine sample will be collected for a drug screen. Subjects will meet with the psychiatrist for weekly assessment and vitals will be collected. In addition, all participants will receive one-hour sessions of manual-driven Medical Management (MM), specifically designed for persons with BPD and substance abuse, provided by an experienced therapist.

Week 4, 8 (~2.5 hours each): Subjects will complete the YMRS, HRSD₁₇, CIWA-Ar, TLFB, IDS-SR₃₀, PACS, PRD-III, AIMS, BAS, SAS, MM, and a urine sample will be collected for a drug screen and pregnancy test. Subjects will meet with the psychiatrist for weekly assessment and vitals will be collected. Blood will be drawn for CBC, CMP, GGT, and CDT.

Week 6 (~2.5 hours): Subjects will complete the YMRS, HRSD₁₇, CIWA-Ar, TLFB, IDS-SR₃₀, PACS, PRD-III, AIMS, BAS, SAS, GNG, MM, and a urine sample will be collected for a drug screen. Subjects will meet with the psychiatrist for weekly assessment and vitals will be collected.

Week 12 (~3.5 hours): Subjects will complete the YMRS, HRSD₁₇, CIWA-Ar, TLFB, IDS-SR₃₀, PACS, PRD-III, AIMS, BAS, SAS, GNG, BIS-11, MM, and a urine sample will be collected for a drug screen and pregnancy test. Subjects will meet with the psychiatrist for weekly assessment and vitals will be collected. Blood will be drawn for CBC, CMP, hs-CRP, GGT, CDT, lipids, and for aripiprazole levels. An exit survey will also be administered to participants evaluating their perception of in-person vs. virtual study visits. In the event of early discontinuation, the survey will be administered at the last available study visit.

At the end of the week 12 treatment phase, participants in both treatment arms who are taking 15 mg/day of aripiprazole (or placebo) and with at least one heavy drinking day will be asked to continue in a 4-week extension phase. Participants taking 3A4 or 2D6 inhibitors will be excluded from this phase. Those in the active treatment group will be increased to 30 mg/day while those in the placebo arm will remain on placebo.

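### Exploratory 6 compares continuous week-16 laboratory values without the week-12 adjustment it gives outcome and side-effect scores, so arm differences present before the dose increase pass in full into the test

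*Combined protocol and SAP*

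**What the plan says.** Section 14, Exploratory 6, states the purpose: "Explore safety, tolerability and efficacy of an increase in aripiprazole from 15 mg to 30 mg". It then sets two different analyses for week 16.

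- Laboratory and other safety measures: "All lab values and other safety measures will be compared between treatment groups at week 16 using t-test or chi-square test, as appropriate". No covariate or change score is named.
- Outcome measures and side-effect scales (the BAS is the example given): these "will be compared between groups at week 16 using analysis of covariance", and "Week 12 value of the outcome will be the covariate".

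Section 4 defines who has week-16 data. The extension is open, in either arm, only to people who have reached 15 mg/day or its placebo equivalent. The drinking criterion is that those "with at least one heavy drinking day will be asked to continue in a 4-week extension phase". Users of 3A4 or 2D6 inhibitors and of strong CYP3A4 inducers are left out. The original arms carry over: "Those in the active treatment group will be increased to 30 mg/day while those in the placebo arm will remain on placebo". No new randomisation is described.

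Section 3 gives a different drinking criterion: "Participants with ≥ 1 drinking day at week 12 will be enrolled in a 4-week extension phase".

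Section 4 also lists the blood draws. CBC, CMP, GGT and CDT are taken at both week 12 and week 16. In Section 14, CDT, GGT, AST and ALT are also named as secondary outcomes under the Primary Aim.

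**The concern.** The question is what happens after the increase, so week 12 is the natural reference point. The plan uses it for drinking and side-effect scores but not for laboratory values. Two things can separate the arms before the increase starts.

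1. **Earlier treatment.** The active arm has had 12 weeks of aripiprazole. The protocol itself expects laboratory effects: Section 10 lists raised blood sugar among the frequent risks, and the alcohol markers are outcomes that the drug is hoped to change.
2. **Selection.** Entry depends on week-12 drinking and on the dose reached. Both come after randomisation and both can be affected by treatment, so randomisation no longer guarantees comparable arms.

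A week-16 t-test cannot tell a difference built up by week 12 from one that arose later. A reader could take an old difference for an effect of the higher dose, or an opposite earlier difference could hide a real change.

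**Working it through.** **Stated figure.** The plan gives no sample size, SD, effect or power for the week-16 comparison, so there is nothing to reproduce. The only ceiling is the planned total of 132, about 66 per arm.

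**Assumed inputs** (none is in the documents):
- Extension size n: 20, 30 or 40 per arm. This is 20/66 = 30% to 40/66 = 61% of an arm.
- Arm difference at week 12, persisting unchanged: d = 0.3 SD, with 0.5 SD as a second case.
- Correlation between week 12 and week 16: ρ = 0.5 to 0.8.
- True added effect of the increase: 0.
- Two-sided alpha: 0.05.

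**Step 1. The planned t-test.** Its expected estimate is d, all of it carried over. The rejection probability comes from the noncentral t distribution with 2n − 2 degrees of freedom and noncentrality d√(n/2). For d = 0.3 these are 0.3√10 = 0.95, 0.3√15 = 1.16 and 0.3√20 = 1.34.

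**Step 2. ANCOVA on week 12.** When each visit is a stable patient component plus independent noise, the slope on the week-12 value is ρ. The share left over is then d(1 − ρ):
- ρ = 0.5: 0.3 × 0.5 = 0.15 SD
- ρ = 0.7: 0.3 × 0.3 = 0.09 SD
- ρ = 0.8: 0.3 × 0.2 = 0.06 SD

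Residual variance falls to 1 − ρ², which is 0.75 at ρ = 0.5 and 0.36 at ρ = 0.8.

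**Step 3. Change from week 12.** The expected estimate is d − d = 0.

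**Results for d = 0.3.** The t-test column is exact. The others come from 2,000 simulated trials per setting, with a standard error of about 0.5 to 0.7 percentage points.

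| Per arm | t-test rejects | ANCOVA rejects (ρ = 0.5 / 0.7 / 0.8) | Change rejects (same ρ) |
|---|---|---|---|
| 20 | 15% | 8% / 6% / 7% | 4% / 5% / 6% |
| 30 | 21% | 10% / 7% / 6% | 5% / 5% / 5% |
| 40 | 26% | 11% / 9% / 7% | 5% / 6% / 5% |

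For d = 0.5 the t-test rejects in 34%, 48% and 60%. With 30 per arm and d = 0.5, ANCOVA rejects in about 20% at ρ = 0.5 and 9% at ρ = 0.8. Change from week 12 stays near 5%.

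**Step 4. Control case.** With d = 0 and no selection, the simulated t-test rejects in 4.4% to 6.0%, in line with 5%. The test itself is sound. The problem lies in what it is asked to compare.

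**Step 5. Selection alone.** Assume that the drug lowers week-12 drinking by 0.5 SD and that 30% to 70% of placebo patients meet the entry criterion. Then about 15% to 51% of active patients meet it. Take a prognostic factor that the drug does not affect and that correlates 0.3 to 0.7 with drinking. It differs between the selected arms by about 0.09 to 0.27 SD.

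**The case against.** The strongest reply is that this is the sixth of seven exploratory analyses. It touches neither the primary nor the secondary aim, nor the sample size, and the DSMB's flag in Section 11 rests on SAE counts. The absolute laboratory level after escalation, against placebo, is also a coherent safety contrast. All of that stands, and it sets the weight of the point. It does not remove the mismatch between the aim, which is about the increase, and a test that ignores where each patient stood when the increase began.

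Several stronger readings are tempting and are not supported:

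- *All week-16 safety data are unadjusted.* Side-effect scales already have the week-12 covariate. The clear gap is CBC and the CMP components other than AST and ALT.
- *GGT, CDT, AST and ALT are definitely unadjusted.* As laboratory values they fall under the t-test, but as alcohol outcomes they could fall under ANCOVA. The text does not settle it.
- *The plan will attribute week-12 differences to the higher dose.* The aim's wording invites that reading, but the plan states no rule of attribution.
- *The error rate is known to be inflated.* Every figure above depends on an assumed difference and an assumed extension size.
- *ANCOVA would cure the problem.* It leaves about a (1 − ρ) share of a pre-existing difference. Neither ANCOVA nor a change score restores randomisation.

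**Conclusion.** The point holds for continuous laboratory values. They are compared at week 16 without adjustment, in a subset selected after randomisation, although the plan already uses week 12 as the reference for other measures and the needed values are collected.

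A persisting week-12 difference passes through in full. If it is 0.3 SD, the false-positive rate for an added effect of the increase is about 15% to 26% at 20 to 40 per arm. ANCOVA would leave 0.15 to 0.06 SD of it at correlations of 0.5 to 0.8. These sizes illustrate the mechanism and are not estimates for this trial.

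No analysis of these data can isolate 30 mg versus 15 mg, because no arm stays on 15 mg. Even change from week 12 mixes the increase with four more weeks of exposure. Severity is low and the primary conclusion is unaffected.

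**What to change.** Amend Exploratory 6 in Section 14 as follows.

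1. For continuous laboratory measures drawn at both visits (CBC, CMP, GGT, CDT), use ANCOVA with the week-12 value as covariate, as the plan already does for outcome and side-effect scores.
2. Report change from week 12 by arm, with intervals, beside the ANCOVA, because of the (1 − ρ) remainder.
3. For categorical laboratory measures, tabulate shifts from week 12 to week 16 by arm.
4. State that GGT, CDT, AST and ALT follow the same ANCOVA, so that each variable has one planned test.
5. Label the result as the escalated active arm versus placebo in a selected subset, and not as a randomised estimate of 30 mg versus 15 mg.
6. Reconcile the entry criterion. Section 1 and Section 4 refer to heavy drinking days, while Section 3 and Section 14 refer to any drinking day. Also reconcile the timing of the increase, which Section 1 places at week 12 and the Exploratory 6 heading in Section 14 places at week 16. The analysis set and the reference visit depend on both.

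Adding the randomisation strata or baseline drinking as covariates is optional. Baseline drinks per drinking day is already a stratum, and the subset may be small.

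The cost is SAP wording, a few more tables and a narrower conclusion for one exploratory aim. No new visit or sample is needed.
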